8.1.2 Sensitivity Analysis I

Missing value is allowed. No need to check missing value. All the missing values during the treatment period will be considered as no-smoking.

Sensitivity analysis I endpoint calculation:

- Only subjects with adequate data that they were smoking during Week 4 to Week 7 are set as non-abstinent.
 - There is smoking in the self-report
 - Or subject has exhaled CO level of greater or equal to 5 ppm using the Vitalograph Breath CO monitor in the office at scheduled Week 5 and Week 7.

Protocol 405-201-00055 Statistical Analysis Plan

- Subjects lost to follow-up/Early termination will be set as non-abstinent.
- All other subjects having missing value in CO value and self-report will be set as abstinent.

A descriptive statistic will be provided with 90% binomial confidence intervals.

For all binomial confidence intervals, it is based on normal approximation. If the number of abstinent or the number of non-abstinent ≤ 5 , we will use the exact method.

8.1.3 Sensitivity Analysis II

Two missing in self-report are allowed.

Sensitivity Analysis II endpoint calculation:

- Set it as four-week continuous abstinence:
 - If there is no smoking in the self-report.
 - And if subject has exhaled CO level of less than 5 ppm using the Vitalograph BreathCO monitor in the office at scheduled Week 5 or Week 5 value is missing.
 - And if subject has exhaled CO level of less than 5 ppm using the Vitalograph BreathCO monitor in the office at scheduled week 7
 - Missing value check:
 - For CO value, only one missing value is allowed, and Week 7 value cannot be missing.
 - For self-report value, only two missing in each visit week (7 days) is allowed.
- All the others will be set as non-abstinent.
 - Week 7 CO value is missing.
 - Three or more missing in Self-report every visit week (7 days)
 - Lost to follow-up/Early termination
 - Subjects with adequate data that they were smoking

A descriptive statistic will be provided with 90% binomial confidence intervals.

For all binomial confidence intervals, it is based on normal approximation. If the number of abstinent or the number of non-abstinent ≤ 5 , we will use the exact method.

8.1.4 Sensitivity Analysis III

Three missing in self-report are allowed.

Sensitivity Analysis III endpoint calculation:

Protocol 405-201-00055 Statistical Analysis Plan

- Set it as four-week continuous abstinence:
 - If there is no smoking in the self-report.
 - And subject has exhaled CO level of less than 5 ppm using the Vitalograph BreathCO monitor in the office at scheduled Week 5 & Week 7
 - Missing value check:
 - For CO value, only one missing value is allowed, and Week 7 value cannot be missing.
 - For self-report value, only three missing in every visit week (7 days) is allowed.
- All the others will be set as non-abstinent.
 - Week 7 CO value is missing.
 - Four or more missing in self-report every visit week (7 days)
 - Lost to follow-up/Early termination
 - Subjects with adequate data that they were smoking

A descriptive statistic will be provided with 90% binomial confidence intervals.

For all binomial confidence intervals, it is based on normal approximation. If the number of abstinent or the number of non-abstinent ≤ 5 , we will use the exact method.

8.2 Secondary Outcome Endpoint

Secondary outcome variable is the incidence of nausea at any timepoint after drug administration begins.

8.2.1 Secondary Efficacy Analysis

The nausea is only considered when it is a treatment-emergent adverse event (TEAE). The number of subjects with nausea is analyzed. The incidence rate of nausea will be tabulated in the frequency percentage.

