PROTOCOL NUMBER

405-201-00055

EXECUTIVE SUMMARY

This single-group, open-label study of 50 subjects will explore the potential of centanafadine in promoting smoking abstinence in adult smokers seeking to quit. The efficacy and tolerability of centanafadine at a dose of 400 mg total daily dose (TDD) (200 mg twice daily [BID]) approximately 4 to 6 hours apart (during a 7-week treatment period) will be compared with a benchmark of abstinence based on historical data from clinical trials of varenicline, viewed as the most efficacious pharmacotherapy currently approved by the FDA.

OBJECTIVES AND ENDPOINTS

[figure not shown]
The primary endpoint is the four-week continuous abstinence rate of subjects with the treatment of centanafadine during weeks 4-7. A participant is considered abstinent from combustible cigarettes if he or she self-reports tobacco abstinence (no cigarette smoking, not even a puff) assessed by responses to daily messages throughout the period and has an exhaled carbon monoxide (CO) level of less than 5 ppm using the Vitalograph BreathCO monitor in the office at Visit 5 and Visit 6.

A secondary objective will be to determine if centanafadine yields equivalent efficacy to that of varenicline, with a significant reduction in the incidence of nausea the most prevalent side effect reported following varenicline treatment. Incidence rate of nausea is assessed by self-reported side effects collected via an open-ended question at each study visit.

STUDY DESIGN

This single-group, small-scale, open-label study (N= 50) will evaluate centanafadine SR (400 TDD) as a potential smoking cessation treatment. Participants enrolled in the study will be given centanafadine SR at a dose of 400 mg TDD (200 mg BID) approximately 4 to 6 hours apart for seven weeks.

The study will consist of up to a 28-day screening period, a baseline visit, a 7-week treatment period, and a 7-day safety follow-up period.

DOSING RATIONALE

The 400 mg TDD of centanafadine SR oral tablets (200 mg BID) will be evaluated in this study. This dose was found to produce a significant blockade (>10%) of transporters for serotonin, dopamine, and norepinephrine as well as alleviating symptoms of inattention and hyperactivity/impulsivity in patients with ADHD, without inducing a high incidence of nausea and headache that occur with doses as high as 800 mg.¹

SAMPLE SIZE ESTIMATION

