Given the conditional logic of the phase one analyses, Monte Carlo simulations based on a sample size of 50 were conducted to determine the significance thresholds for the binomial tests so that the overall Type I error rate across all tests would be 10% (9.87% of 100,000 simulated datasets), assuming the null hypothesis that centanafadine yields a four-week continuous smoking abstinence rate of 50% and an overall incidence of nausea of 30%. The power of the phase one analyses (probability of moving to phase two) was also determined by Monte Carlo simulations for three scenarios. In the first scenario, the treatment has a higher four-week continuous abstinence rate at 6 weeks post target quit date (65%) than varenicline, but an equivalent rate of nausea (30%). Power under this scenario is about 74%. In the second scenario, the treatment has the same four-week continuous abstinence rate at 6 weeks post target quit date as varenicline (50%) but has a lower nausea rate (15%). Power under this scenario is about 76%. Last, if the treatment generates both a higher four-week continuous abstinence rate at 6 weeks post target quit date (65%) and a lower rate of nausea (15%) then power is about 94%.

STATISTICAL METHODS

The estimation of the four-week continuous smoking abstinence rate at 6 weeks post target quit date is around 50% and 30% of treated individuals experiencing nausea from varenicline treatment based on the historical studies.² The smoking abstinence rate during weeks 4-7 will be calculated with 90% binomial confidence intervals, and the incidence rate of nausea will be tabulated, which will be compared with the thresholds established for efficacy and tolerability.

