There are currently seven Food and Drug Administration (FDA)-approved smoking cessation medications, which fall into three main categories: nicotine replacement therapy (NRT) including nicotine patch, gum, lozenge, inhaler, and nasal spray; varenicline (Chantix); and bupropion (Zyban/Wellbutrin). Among US smokers, 29.1% use NRT when attempting to quit smoking whereas only 7.9% use varenicline and 2.4% use bupropion.^{8,9} Two other medications that show some efficacy, clonidine and nortriptyline, are not FDA approved, and account for less than 1% of smoking cessation treatment.¹⁰ None of the current treatments yields sustained abstinence rates of over 25% at one year, but varenicline is the most efficacious. Varenicline is a full agonist on $\alpha 7$ -nicotinic acetylcholine receptors (nAChRs) and a partial agonist on the $\alpha 4\beta 2$, $\alpha 3\beta 4$, and $\alpha 6\beta 2$ subtypes.^{2,11,12} Smoking abstinence rates at weeks 9-12 in two Phase III trials of varenicline were nearly identical at 44%. Given that four-week continuous abstinence at weeks 4-7 will be taken to be the primary abstinence outcome in the present study, and modeling relapse curves over the initial weeks of abstinence suggests that abstinence rates are ~5% higher at 6 weeks than at 12 weeks after the target quit-smoking date,¹³ in this study a slightly higher rate of 50% abstinence will be taken to be the benchmark criterion to meet or exceed. Common adverse events associated with varenicline include nausea, insomnia, abnormal dreams, headaches, and nasopharyngitis.¹⁴ The most common adverse reaction reported is nausea, with 30-40% of participants in randomized control trials reporting mild to moderate levels of nausea.¹⁵ Discontinuation/drop-out rates of nearly 10% have been noted during clinical trials due to these adverse effects.¹⁶ In real-world settings, discontinuation of varenicline treatment may be as high as 57%.⁸

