4.6 DISCONTINUATION OF PARTICIPANTS FROM STUDY

Discontinued participants will include both participants who withdraw from the study (participant's decision) or participants who are discontinued from the study (following Investigator's decision). A participant can only be discontinued from the study after the IMP is dispensed to them. Participants that are not dispensed the IMP are considered screen failures.

Participants will be informed that they are free to withdraw from the study at any time. Participants should be questioned for the reason of premature withdrawal from the study, although they are not obliged to disclose it.

Participants discontinued from the study cannot re-enter the study.

Participants will be discontinued from the study for any of the following reasons:

- Withdrawal of informed consent.
- Any adverse effect or condition that would jeopardize continued safe study participation.
- Discontinuation is considered to be in the best interest for the participant or for other participants participating in the study, as judged by the Investigator or designee.

Participants may be discontinued from the study for any of the following reasons based on the judgment of the Investigator:

- No-show to appointments and unable to reschedule within the visit window.
- The misuse or abuse of study related equipment.
- Potential loss of the participant's data validity.
- Unwilling or unable to comply with study procedures.

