11.3.1 Smoking Abstinence

Complete abstinence from combustible cigarette use at each time point will be defined by a self-report of no cigarette smoking (not even a puff) since the prior session, confirmed by an expired air CO reading of less than 5 ppm. The primary outcome will be four-week continuous smoking abstinence during weeks 4-7. An intent-to-treat approach will be taken in which any participants lost to follow-up after receiving the investigational product, or who have smoked during weeks 4-7 will be counted as non-abstinent.

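### An early leaver who cannot be reached and has no recorded nausea is counted by default as nausea-free, which makes the tolerability threshold easier to pass; add a descriptive bounding row.

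*SAP*

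**What the plan says.** The secondary outcome is nausea at any time after dosing starts (Protocol 11.3.2; SAP 6.2 and 8.2). SAP 8.2.1 uses nausea only when it is a TEAE: "The number of subjects with nausea is analyzed", and the result is shown as a percentage. SAP 8.2.1 names no analysis set, but the Safety Analysis Set and the Full Analysis Set (SAP 5.2, 5.3) both contain everyone who took a dose, and the SAP's AE tables use the former. SAP 5.5 and Protocol 10.4 rule out imputation.

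For abstinence, Protocol 11.3.1 counts "any participants lost to follow-up after receiving the investigational product" as non-abstinent. SAP 8.1.1 extends this to early termination, and SAP 8.1.2 to 8.1.4 add three sensitivity analyses on missing data. Nausea has no drop-out rule and no sensitivity analysis.

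On leaving, Protocol 4.6 states: "Participants should be questioned for the reason of premature withdrawal from the study, although they are not obliged to disclose it". The Schedule of Events has no early-termination visit. Its first AE interview on drug is V3.

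The nausea rate bears on a decision. The Synopsis (Sample Size Estimation) sets binomial thresholds under a null of "a four-week continuous smoking abstinence rate of 50% and an overall incidence of nausea of 30" per cent, and Protocol 11.2 compares the nausea rate with a tolerability threshold. SAP 8.2.1 itself has no test, interval or threshold.

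**The concern.** No sentence says that drop-outs are nausea-free. It follows from three rules together: the numerator is recorded events, the denominator is everyone dosed, and nothing is imputed. For someone who stops reporting, silence is scored against the drug on abstinence and in its favour on nausea.

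The error on nausea runs one way, since a case that is never recorded can only lower the observed rate. Nausea is also a plausible reason to stop: Protocol 7.3.1 lists it among the common adverse effects of centanafadine. At stake is a conclusion that nausea is below the 30% benchmark when part of the difference comes from participants whose nausea status after leaving is unknown.

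**Working it through.** **Inputs.** From the Synopsis: n = 50, one arm; null 50% abstinent and 30% nausea; overall Type I error 9.87% by simulation (100,000 datasets); power about 74% (65% abstinent, 30% nausea), 76% (50%, 15%) and 94% (65%, 15%). Protocol 11.1 is blacked out, so the thresholds are not available. The unreported share of nausea is not in the documents either and is varied below.

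**Step 1: reproduce the plan's figures.** Let A be the number abstinent and N the number with nausea, both binomial with n = 50. A rule that fits is: pass if A ≥ 31, or if A ≥ 20 and N ≤ 9.

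P(pass) = P(A ≥ 31) + P(20 ≤ A ≤ 30) × P(N ≤ 9)

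- 65% / 30%: 0.7264 + 0.2735 × 0.0402 = 73.7% (stated 74%)
- 50% / 15%: 0.0595 + 0.8811 × 0.7911 = 75.7% (stated 76%)
- 65% / 15%: 0.7264 + 0.2735 × 0.7911 = 94.3% (stated 94%)
- Null 50% / 30%: 0.0595 + 0.8811 × 0.0402 = 9.5% (stated 9.87%)

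The powers match. The Type I error does not match exactly: the Monte Carlo standard error is √(0.0987 × 0.9013 / 100,000) = 0.09 points, so the gap is about 4 standard errors. The sponsor's rule is therefore close to this one but not identical. A lower abstinence limit of 19 fits about as well (73.7%, 77.8%, 94.3%; error 9.6%). Every single-tier rule that fitted put the nausea cut at 9 of 50.

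**Step 2: chance of passing the nausea cut at a true rate of 30%.** If a share u of cases is never recorded, the observed rate is 0.30 × (1 − u).

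| u | Observed rate | P(N ≤ 9) |
|---|---|---|
| 0 | 30% | 4.0% |
| 5% | 28.5% | 6.4% |
| 10% | 27% | 9.8% |
| 20% | 24% | 20.7% |

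If drop-outs have the same 30% nausea as others and none of theirs is recorded, u equals the drop-out rate. If half of theirs is recorded, u is half the drop-out rate. The direction does not depend on the cut: at u = 10%, a cut of 8 goes from 1.8% to 5.0%, and a cut of 10 from 7.9% to 17.0%.

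**Step 3: overall error of the inferred rule.** This depends on what drop-out does to abstinence.

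- Abstinence stays at 50% with drop-outs already counted as failures: 0.0595 + 0.8811 × 0.0979 = 14.6% at u = 10%, and 0.0595 + 0.8811 × 0.2066 = 24.1% at u = 20%.
- Abstinence is 50% among completers only, so 45% or 40% overall at 10% or 20% drop-out, with none of the drop-outs' nausea recorded: 0.0116 + 0.7910 × 0.0979 = 8.9%, and 0.0014 + 0.5521 × 0.2066 = 11.5%. These treat the two counts as independent. Simulation with the same drop-outs in both counts gives 8.6% and 10.3%.

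In the second case overall error with full capture would be only 4.3% and 2.4%. In that simulation the tolerability route alone (A ≥ 20 and N ≤ 9) still rises, from 3.2% to 7.5% at 10% drop-out and from 2.2% to 10.2% at 20%.

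**The case against.** The plan does more to capture nausea among leavers than SAP 8.2.1 suggests. Protocol 3.1 and SAP 3.1 ask all participants to take a safety call seven days after the last dose, and Protocol 6.6.8 includes an AE review in that call. Protocol 6.6.7 adds calls on Day 1 and in Weeks 2, 4 and 6; 4.7 requires three contact attempts; 7.5 gives a 24-hour number. A reader might infer that an early leaver has no later AE interview. The documents do not support that. The gap is confined to those who cannot be reached or who decline. It does remain: the call is only requested, Protocol 6.6.8 times it from V6, which an early leaver does not attend, and nothing says how an unreached participant is scored.

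A reader might also infer that withholding the reason for leaving makes someone nausea-free. It does not. Nausea comes from the AE question, and nausea already recorded still counts.

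The protocol's background figure, "Discontinuation/drop-out rates of nearly 10% have been noted during clinical trials due to these adverse effects", concerns varenicline and discontinuations whose cause was known. It is not evidence of silent drop-out on centanafadine and supports none of the values of u above.

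Finally, the benchmark is itself an as-reported rate (Protocol 1.1). If the historical trials also scored unreported nausea as absent, part of the bias is shared. The documents do not say. This stands as a limit on both the concern and the remedy.

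**Conclusion.** The asymmetry is real and its direction is certain: unreported nausea among unreachable leavers lowers the observed rate and makes the comparison with 30% easier to pass. Its size is unknown. The range of 4.0% to 20.7% for passing the nausea cut rests on an inferred cut of 9 of 50 and an assumed unreported share of 0 to 20%.

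A tempting stronger reading is that the trial's overall Type I error rises to 14.6% or 24.1%. The documents do not establish this. It requires abstinence to stay at 50% despite drop-outs being scored as failures. If drop-outs pull abstinence down, overall error stays around 9% to 12% under the inferred rule, near the nominal 10%. The point is a modest one: the plan should show whether the nausea conclusion depends on drop-outs.

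**What to change.** In SAP 8.2.1, name the Safety Analysis Set as the denominator and keep the observed n/N as the main estimate. Add one descriptive sensitivity row that counts as nausea every dosed participant who left before V6, had no AE review at or after leaving, and has no recorded nausea. Show how many such participants there are. If the comparison with the tolerability threshold differs between the two rows, report the nausea conclusion as dependent on drop-outs.

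Do not make the bound a condition for the claim. With true nausea of 15% and 10% unexplained drop-out, the bounded rate is 0.90 × 0.15 + 0.10 = 23.5%, P(N ≤ 9) falls from 79% to 23%, and power in the lower-nausea scenario falls from 76% to 0.0595 + 0.8811 × 0.2306 = 26% under the inferred rule.

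The cost is one table row from disposition and AE data already collected. The downside is that the bound is conservative and not like-for-like with an as-reported 30% benchmark; a note beside the row should say so.

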8.3 Other Efficacy Analyses

The other efficacy endpoints include:

- CCI
- [REDACTED]
- [REDACTED]

Protocol 405-201-00055 Statistical Analysis Plan

- CCI [REDACTED]
- [REDACTED]
- Abstinence rate by Week
- Four-week continuous abstinence rate using exhaled CO level
- Four-week continuous abstinence rate using self-report
- Summary of CO Level
- Number of cigarettes daily

8.3.1 CCI [REDACTED]

CCI [REDACTED]

8.3.2 CCI [REDACTED]

CCI [REDACTED]

Protocol 405-201-00055 Statistical Analysis Plan

CCI

8.3.3 CCI

CCI

8.3.4 CCI

CCI

8.3.5 CCI

CCI

8.3.6 Abstinence Rate by Week

Abstinence rate calculation:

- If subject has exhaled CO level of less than 5 ppm using the Vitalograph BreathCO monitor and there is no smoking in the self-report, then set it as abstinence.
 - Missing value check:
 - For CO value, value can be missing.
 - For self-report value, only one missing in every visit week (7 days) is allowed.

Protocol 405-201-00055 Statistical Analysis Plan

- All the others will be set as non-abstinent.
 - There are two or more missing in self-report every visit week (7 days)
 - Lost to follow-up/Early termination
 - Subjects with adequate data that they were smoking

A descriptive statistic will be provided with 90% binomial confidence intervals by week.

For all binomial confidence intervals, it is based on normal approximation. If the number of abstinent or the number of non-abstinent ≤ 5 , we will use the exact method.

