6.5.10 Expired Air CO Breath Test

Carbon Monoxide (CO) in participant's exhaled breath (expressed as ppm) will be measured using a Vitalograph BreathCO Monitor. Participants must have an expired air CO reading at V1 of at least 10 ppm for inclusion into this study. This test will be repeated at each of the visits.

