6.6.7 Telephone Contact

Participants will be contacted via phone on Day 1 (first day of IMP) and on weeks that they are not scheduled to visit the Center (Wk 2, Wk 4, and Wk 6) to ask how they are doing and answer any questions the participant may have.

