CT-3.4 Medical History (Enrolled Analysis Set)

CT-4.1 Concomitant Medications: Medications Taken Prior to Start of Study Therapy (Enrolled Analysis Set)

CT-4.2 Concomitant Medications: Medications Taken During Study (Enrolled Analysis Set)

CT-5.1.1.1 Smoking Continuous Abstinence Rate During Week 4-7 (Full Analysis Set)

CT-5.1.1.2 Smoking Continuous Abstinence Rate During Week 4-7 - Sensitivity Analysis I (Full Analysis Set)

CT-5.1.1.3 Smoking Continuous Abstinence Rate During Week 4-7 - Sensitivity Analysis II (Full Analysis Set)

CT-5.1.1.4 Smoking Continuous Abstinence Rate During Week 4-7 - Sensitivity Analysis III (Full Analysis Set)

CT-5.1.1.5 Smoking Continuous Abstinence Rate During Week 4-7-Using Only Exhaled Carbon Monoxide Level (Full Analysis Set)

[figure not shown]
CT-5.1.1.6 Smoking Continuous Abstinence Rate During Week 4-7 - Using Only Self-report (Full Analysis Set)

CT-5.1.2 Summary of Non-smoking Rate from Self-report and CO Level by Week (Full Analysis Set)

Protocol 405-201-00055 Statistical Analysis Plan

[figure not shown]
CT-5.1.3 Summary of Non-smoking Rate from Self-report by Week (Full Analysis Set)

CCI

Protocol 405-201-00055 Statistical Analysis Plan

CCI

CT-6.1.1 Expired Air CO breath Test Result (Full Analysis Set)

CT-6.1.2 Summary of Subjects with CO Level Greater Than or Equal to 5 PPM (Full Analysis Set)

CT-6.2 Summary of Change from Baseline in Average Number of Cigarettes Smoked Per Day by Week (Full Analysis Set)

CT-7.1 Extent of Exposure (Safety Analysis Set)

CT-7.2 Number and Percentage of Subjects Receiving Study Medication and Mean and Range of Average Daily Dose (Safety Analysis Set)

CT-8.1 Incidence of Adverse Events (All Causalities) (Safety Analysis Set)

Protocol 405-201-00055 Statistical Analysis Plan

CT-8.2.1 Incidence of Treatment-emergent Adverse Events by System Organ Class and MedDRA Preferred Term (Safety Analysis Set)

CT-8.2.2 Incidence of Treatment-emergent Adverse Events by System Organ Class, MedDRA Preferred Term and Severity (Safety Analysis Set)

CT-8.2.2.1 Incidence of Treatment-emergent Adverse Events Greater Than or Equal to 5% by System Organ Class and MedDRA Preferred Term (Safety Analysis Set)

CT-8.2.2.2 Incidence of non-Serious Treatment-emergent Adverse Events Greater Than or Equal to 5% by System Organ Class and MedDRA Preferred Term (Safety Analysis Set)

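### The weekly abstinence rate (SAP 8.3.6) passes a participant whose CO is missing, against the CO-confirmed definition at visits where CO is scheduled

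*SAP*

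**What the plan says.** SAP 8.3.6 opens with a two-part test: "If subject has exhaled CO level of less than 5 ppm using the Vitalograph BreathCO monitor and there is no smoking in the self-report". Its missing-value check then relaxes one part completely and the other slightly. For CO: "For CO value, value can be missing". For the daily messages: "For self-report value, only one missing in every visit week (7 days) is allowed". Its reasons for non-abstinence are two or more missing reports in the week, loss to follow-up or early termination, and data showing smoking. A missing CO is not among them. The output is listed in SAP section 17 as "CT-5.1.2 Summary of Non-smoking Rate from Self-report and CO Level by Week (Full Analysis Set".

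Protocol 11.3.1 sets the definition: "Complete abstinence from combustible cigarette use at each time point will be defined by a self-report of no cigarette smoking", running from the previous session and "confirmed by an expired air CO reading of less than 5 ppm". It makes no exception for an absent reading.

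On when CO is measured, protocol 6.5.10 says "This test will be repeated at each of the visits", and the schedule of events shows no CO outside clinic visits. Protocol 6.6.7 provides telephone contact "on weeks that they are not scheduled to visit the Center (Wk 2, Wk 4, and Wk 6".

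SAP section 1 states that the SAP is consistent with protocol version 3.0, and section 14 records no changes to the planned analyses.

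**The concern.** The table title promises a rate based on self-report and CO, but a participant who gave no breath sample can be counted as abstinent in it. Where a CO was due, that is weaker than the protocol's definition. It also lets one participant be abstinent for Week 7 in CT-5.1.2 and non-abstinent in the primary table CT-5.1.1.1, solely because the Week 7 CO is missing.

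The series is also not on one footing across weeks. A reader who sees the rate rise in weeks without CO and fall in weeks with it could take a change in verification for relapse and recovery. At stake is the reading of one descriptive curve, not the primary result.

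**Working it through.** **1. The plan's own precision figure.** SAP Table 4-1 is the only visible statement of precision for an abstinence rate. The exact (Clopper-Pearson) 90% interval for n = 50 reproduces all four rows to five decimals; at a proportion of 0.5 it is 0.37625 to 0.62375. The half-width is 0.24751/2 = 0.124, about 12 points. The normal approximation planned for the weekly rates gives 0.38369 to 0.61631, also about 12 points. This serves only as a yardstick; the SAP gives no such figure for the weekly rates.

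**2. How each rule treats a missing CO.**

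| Rule | CO missing at Week 5 | CO missing at Week 7 |
|---|---|---|
| Protocol 11.3.1 | not confirmed | not confirmed |
| SAP 8.1.1 (primary) | tolerated (one missing CO allowed) | non-abstinent |
| SAP 8.3.7 (CO only) | non-abstinent | non-abstinent |
| SAP 8.3.6 (weekly) | can pass | can pass |

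**3. CO assigned by scheduled visit.** On treatment, CO is due at V3, V4, V5 and V6, nominally Weeks 1, 3, 5 and 7. Weeks 2, 4 and 6 have none. So 4 of 7 weeks have a scheduled CO and 3 of 7 rest on self-report. Within a visit week, unverified participants enter only through missed tests.

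**4. CO assigned by trial day.** Table 5.4-1 is titled for efficacy analysis, and SAP 5.4 sets trial day = assessment date − first-dose date + 1. The visit windows then give:

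| Visit | Days after first dose | Trial days | Mapped week |
|---|---|---|---|
| V4 | 21 ± 3 | 19-25 | 3 (Days 19-21) or 4 (Days 22-25) |
| V5 | 35 ± 3 | 33-39 | 5 (Days 33-35) or 6 (Days 36-39) |
| V6 | 49 ± 3 | 47-53 | 7 (Days 47-49) or none (Days 50-53) |

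Verified and unverified participants then share a week, and a V6 reading after Day 49 belongs to no week. If three weeks is instead counted as Day 21, V4 spans Days 18-24 and still crosses the Day 21/22 boundary; V5 and V6 likewise cross theirs.

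**5. Size, under assumed inputs.** Let s be the share passing the self-report rule, f the share of those whose CO would be 5 ppm or more, and m the share of those with CO missing in a visit week. With CO assigned by scheduled visit, the 8.3.6 rate is

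- week without CO: s
- visit week: s[(1 − m)(1 − f) + m]
- difference: s·f·(1 − m)

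With s = 50%, the difference in percentage points is:

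| f | m = 0 | m = 20% |
|---|---|---|
| 5% | 2.5 | 2.0 |
| 10% | 5.0 | 4.0 |
| 20% | 10.0 | 8.0 |
| 30% | 15.0 | 12.0 |

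With s = 30% and the same f and m, the range is 1.2 to 9.0 points.

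Within a visit week, the excess over the rate with every CO observed is s·f·m: 0.5 × 0.10 × 0.10 = 0.5 points, or 0.5 × 0.30 × 0.20 = 3.0 points.

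**The case against.** The strongest reply is that a weekly series needs some allowance for absent CO. If a missing CO failed in every week and CO were assigned by scheduled visit, Weeks 2, 4 and 6 would show 0% by construction. That stands, and it rules out simply deleting the allowance.

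A reader might infer that 8.3.6 contradicts the protocol in all seven weeks. The documents do not support this: protocol 11.3.1 counts self-report from the previous session, so it does not clearly govern weeks with only a telephone call. The firm conflict is at scheduled CO visits.

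A reader might also infer that every week's rate mixes verified and unverified participants. That is not established. By scheduled visit, the standard alternates between weeks; mixing from the visit windows arises only with trial-day assignment. SAP 8.1.1 and 8.3.7 refer to scheduled weeks, but 8.3.6 does not say which assignment it uses.

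Nor does the weekly rule depart from the primary rule at Week 5, because 8.1.1 also tolerates a missing Week 5 CO. Only Week 7 differs. There, 8.3.6 still fails early terminators and anyone with two or more missing reports, which limits how many without a reading can pass.

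Finally, the endpoint is descriptive, the allowance is stated openly, and the SAP already lists a self-report weekly table (CT-5.1.3), CO summaries (CT-6.1.1, CT-6.1.2) and a strict CO-only rate (8.3.7). This keeps the point minor. It does not remove the conflict inside 8.3.6 or with protocol 11.3.1.

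**Conclusion.** The point holds in a narrow form and is minor. At scheduled CO visits, 8.3.6 can count an untested participant as abstinent, contrary to protocol 11.3.1; at Week 7 this also contradicts 8.1.1 and 8.3.7. The combined series is CO-verified in some weeks and self-report only in others, with mixing inside weeks as well if trial-day mapping applies.

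The direction is upward wherever CO is absent. The size cannot be determined, since the documents give neither a CO-failure rate among self-reported abstainers nor a rate of missed tests. The 2 to 15 points between weeks without and with CO rest on s = 50%, f = 5-30% and m = 0-20%, all assumed. Inflation from missed tests within a visit week is smaller, 0.5 to 3.0 points in the two cases shown. It would therefore go too far to say that the weekly trend is shown to be distorted: the risk is clear, but its extent is unknown. The primary result has its own CO rule and is unaffected.

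**What to change.** In SAP 8.3.6 and CT-5.1.2:

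- Report the combined rate only at the scheduled CO visits after the quit date: V4, V5 and V6. V3 falls on the day before it.
- Assign CO by nominal visit, not by trial day, and say so.
- Take self-report since the prior visit, keeping the existing tolerance of one missing report per week. For V4, state that the interval starts on the quit day.
- Count a missing CO at these visits as non-abstinent, as 8.3.7 already does for Weeks 5 and 7.
- Show the number of participants with a CO reading at each visit.

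Use CT-5.1.3 (self-report only) for the week-by-week series; it is already planned and applies one standard throughout.

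The cost is SAP wording and fewer rows in one descriptive table, with no new data. Rates will be lower where CO tests are missed. In an assumed case with s = 50%, f = 10% and m = 10%, the rate becomes 0.5 × 0.9 × 0.9 = 40.5%, against 45.5% under the current rule and 45.0% if every CO were observed. The fix thus errs on the low side, in keeping with the intent-to-treat convention of protocol 11.3.1, and the count of readings lets the reader judge by how much.
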